4. ANALYSIS POPULATIONS

Five analysis populations will be used for this study: the Enrolled Population, the Intent-to-Treat (ITT) Population, the Double-blind Safety Population, the Double-blind Discontinuation Population, the Double-blind Discontinuation Safety Population, the Per Protocol (PP) Population.

4.1 Enrolled Population

The Enrolled Population is defined as the group of subjects who sign informed consent.

4.2 Intent-to-treat Population

The ITT Population is defined as the group of subjects who are randomized to a treatment group. Following the ITT principle, subjects in the ITT Population will be analyzed according to their randomized treatment, regardless of the actual treatment received. The ITT population will be used to analyze all efficacy endpoints collected during the double-blind phase.

4.3 Double-blind Safety Population

The Double-blind Safety Population is defined as the group of randomized subjects who received at least one dose of double-blind study drug during the Double-blind Treatment Period. Subjects in the Double-blind Safety Population will be analyzed according to the actual treatment received. The Double-blind Safety Population will be used to analyze all safety endpoints collected during the double-blind phase.

4.4 Double-blind Discontinuation Safety Population

The Double-blind Discontinuation Safety Population is defined as the subset of subjects in the Double-blind Safety Population who have at least one visit in the Discontinuation Period. The Double-blind Discontinuation Safety Population will be used to analyze all endpoints collected during the Discontinuation Period.

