Record dose of ESA and IV iron	X		Record on an ongoing basis						X		
Record number of missed dialysis visits and reason(s)			Record on an ongoing basis								
IV administration of study drug			Record on an ongoing basis								
Inflammatory biomarker samples ^o			X						X		
Adverse event monitoring	X	X	Record on an ongoing basis						X	X	
Concomitant medications (including antipruritic medications) ^p			X	Record on an ongoing basis						X	X
Structured Safety Evaluation ^f		X		X			X			X	

DP = Discontinuation Period; ESA = erythropoiesis-stimulating agent; F = Friday; IV = intravenous; M = Monday; NRS = numerical rating scale; OOWS = Objective Opiate Withdrawal Scale; PRO = patient-reported outcome; Sa = Saturday; ShOWS = Short Opiate Withdrawal Scale; Th = Thursday; Tu = Tuesday; W = Wednesday

-
- a. Each visit during the Double-blind Treatment Period will coincide with the patient's normal dialysis treatments.
 - b. The End-of-Treatment Visit in the Double-blind Phase will be the first dialysis visit following the last dose of study drug (ie, first dialysis on Week 13 [Day 85]), which also corresponds to Day 1 of the Discontinuation Period (DP Day 1).
 - c. Medical history will be updated on Day 1 with any changes since the Screening Visit, and inclusion/exclusion criteria will be confirmed prior to randomization. Antipruritic medication will be updated at each dialysis visit during the Run-in Period.
 - d. Electrocardiogram must be performed prior to the start of dialysis at screening, Day 85 (End of Treatment), or at Early Termination visit.
 - e. Pre-dialysis vital signs, including body temperature, heart rate, and blood pressure, will be recorded on Days 1, 15, 29, 43, 57, 71 and 85 (End of Treatment), or at Early Termination visit only when the patient is in a sitting or semi-recumbent position. Heart rate will be measured at each dialysis; if heart rate is clinically significant and outside the prespecified visits per Schedule of Events, the heart rate will be recorded on the relevant CRF page.
 - f. Pre-dialysis vital signs, including body temperature, heart rate, and blood pressure, will be recorded at each dialysis visit during the Discontinuation Period. Heart rate will be measured at each dialysis.
 - g. Blood samples for clinical laboratory evaluation will be taken at screening, and on Days 1 and 85 (End of Treatment), or at Early Termination visit only.

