4.5 Double-blind Discontinuation Population

The Double-blind Discontinuation Population is defined as the subset of subjects in the Double-blind Safety Population who have completed 12 weeks of treatment, have received at least 6 doses in the 2 weeks prior to the start of the Discontinuation Period, and have at least one visit in the Discontinuation Period. The Double-blind Discontinuation Population will repeat analyses on the endpoints related to drug withdrawal that are also presented for the Double-blind Discontinuation Safety Population.

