5. STUDY SUBJECTS

5.1 Disposition of Subjects

The number of subjects who enrolled, failed screening, were randomized, received treatment, completed treatment, and discontinued from treatment, along with the reason for discontinuation, and number of subjects who entered the Open-label Treatment Period will be presented by treatment group and overall for the Double-blind Treatment Period. Additionally, the number of subjects who entered the Discontinuation Period, completed and discontinued from the Discontinuation Period and the reason for discontinuation will be reported. Subjects randomized will also be reported by the randomization stratification factors.

The following provides the definitions of the aforementioned groups:

- Enrolled subjects are all subjects who sign informed consent.
- Randomized subjects consist of all screened subjects who have a randomization record in the interactive voice/web randomization system.
- Treated subjects are all subjects who received at least one dose of double-blind study drug.
- Subjects who completed treatment are those randomized subjects with a “Yes” noted for the question “Did the subject complete the Double-blind Treatment Period?”.
- Subjects who discontinue treatment early are randomized subjects with “No” noted for the question “Did the subject complete the Double-blind Treatment Period?”. Reasons for treatment discontinuation are also collected on this case report form (CRF).
- Subjects who entered the Discontinuation Period are those who have at least one visit during the Discontinuation Period.
- Subjects who complete the Discontinuation Period are those who have a visit for Day 12 of the Discontinuation Period recorded or were marked as “Yes” to the CRF question “Did the subject complete the whole Double-blind phase of study? (Screening through Discontinuation Period)”
- Subjects who discontinue from the Discontinuation Period are those who entered the Discontinuation Period but do not meet the Discontinuation Period completion criteria above.
- Subjects who entered the Open-label Treatment Period are those who received at least one dose of study drug in the Open-label Treatment Period.

For all categories of subjects (except for enrolled subjects and screen failures), percentages will be calculated using the number of randomized subjects as the denominator.

Additionally, the analysis populations will be summarized in a table by subject counts, as well as in a subject listing:

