- For each questionnaire, the total score at each visit will be computed from the domain scores for each imputed dataset.
- The ANCOVA analysis described above will be implemented for each imputed dataset.
- Results of the ANCOVA on the multiply imputed data sets will be summarized by the SAS MIANALYZE procedure.

Since the observed change from baseline at Week 12 among the non-imputed data will be reported with the MMRM analyses described below, only the LS means, standard errors, 95% CIs, and differences between treatment groups reported with LS means, standard errors, and 95% CIs from the ANCOVA on the imputed data will be reported. The analysis will be completed for both the ITT and PP Populations.

Additionally, the 5-D Itch Scale and the Skindex-10 Scale scores will be analyzed using a mixed effects model with repeated measures (MMRM). The model will contain treatment, week, and treatment-by-week interaction as fixed effects, and baseline score and the randomization stratification variables as covariates. The baseline 5-D total score and the Skindex-10 total score will be defined as the value collected on Day 1, prior to randomization. Repeated measures will include values assigned at the end of Weeks 4, 8, 10, and 12 (end of treatment); see Section [3.1](#) for visit windowing.

It is important to note that, in HD subjects, the study drug administered during the last dialysis of a particular week is not cleared until the first dialysis of the next week. Therefore, measurements that would reflect treatment effect at the end of a specific week (e.g., Week 4) and labelled “end of Week xx” will actually be collected during the first day of the next week (e.g., Week 5).

An unstructured covariance matrix will be used to model the within-subject errors. Should the model fail to converge, a compound symmetric covariance matrix will be used instead. The Kenward-Roger approximation will be used to estimate the denominator degrees of freedom. Missing scores will not be imputed. Assuming that the data are

MAR, the estimates of the treatment differences calculated from the MMRM described above are unbiased.

Standard descriptive statistics will be reported for each time point on the values and changes from baseline along with the least squares (LS) means, standard errors, 95% CIs and differences between treatment groups reported with LS means, standard errors, and 95% CIs.

Worst Itching Intensity ≥ 4 -Point Improvement

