9.2 Adverse Events

The period of adverse event reporting will start after the signing of the informed consent form (ICF) through the study Follow-up Visit or Early Termination Visit (or 7 days after the last dose if no Early Termination Visit was conducted). All adverse events that occur during this reporting period will be collected for all subjects, including subjects who are deemed to be screen failures.

Treatment-emergent adverse events (TEAEs) relative to the Double-blind Treatment Period are identified as any adverse event with an onset date after the first dose of the study drug up to the study End of Treatment/Early Termination Visit or the start of the Discontinuation Period or 7 days after the last dose if no End of Treatment/Early Termination Visit was conducted, whichever is later.

Adverse events that are considered “treatment-emergent” relative to the Discontinuation Period are identified as any adverse event with an onset date after the start of the Discontinuation Period through up to 2 weeks after this time point or the start of the Open-label Treatment Period, whichever comes first.

All tabular adverse event summaries will be for TEAEs by period.

For events with missing start dates, the following criteria will be used:

- If the start date for a particular event is missing, then the event is considered treatment-emergent for the Double-blind Treatment Period, unless the end date is reported and prior to the Double-blind Treatment Period start date.
- If a partial date is consistent with being in more than 1 period, then the ordering of assignment preference will be: Double-blind Treatment Period, Discontinuation Period, and Run-in Period. So if a partial date was consistent with the Double-blind Treatment Period and Discontinuation Period, it would be assigned to the Double-blind Treatment Period.
- If the start time is missing and the start date is the same as the start of a given period, the adverse event will be considered to have occurred in that period.

All adverse events will be coded to SOC and preferred term using the MedDRA version 20.1. The MedDRA treatment dictionary will be used to map adverse events verbatim to SOC and preferred term for standardization and summary purposes.

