DP = Discontinuation Period; EOT = end of treatment; ESA = erythropoiesis-stimulating agent; F = Friday; IV = intravenous; M = Monday; NRS = numerical rating scale; OOWS = Objective Opiate Withdrawal Scale; PRO = patient-reported outcome; Sa = Saturday; ShOWS = Short Opiate Withdrawal Scale; Th = Thursday; Tu = Tuesday; W = Wednesday

- a. Each visit during the Double-blind Treatment Period will coincide with the patient's normal dialysis treatments.
- b. The End-of-Treatment Visit in the Double-blind Treatment Period corresponds to Day 1 of the Discontinuation Period.
- c. Medical history will be updated on Day 1 with any changes since the Screening Visit, and inclusion/exclusion criteria will be confirmed prior to randomization.
- d. Electrocardiogram must be performed at screening, and Day 85 prior to the start of dialysis.
- e. Vital signs, including body temperature, heart rate, and blood pressure, will be obtained at the specified visits when the patient is in a sitting or semi-recumbent position prior to the start of dialysis. Heart rate will be collected at each dialysis; if clinically significant and outside the prespecified visits per SOE, the heart rate will be recorded on the relevant CRF page.
- f. Pre-dialysis vital signs will be recorded on Days 1, 15, 29, 43, 57, and 85 only.
- g. Vital signs, including body temperature, heart rate, and blood pressure, will be obtained prior to the start of each dialysis at each dialysis visit during the Discontinuation Period.
- h. Blood samples for clinical laboratory evaluation will be taken on Days 1 and 85 only.
- j. Training on Worst Itching Intensity NRS on the first day of the Run-in Period.
- k. Training on Skindex-10 Scale and 5-D Itch Scale may be performed at any time during the week prior to randomization or on Day 1 of the Double-blind Treatment Period.
- l. Patients will be requested to complete their worksheets each day at a similar time (either at home on non-dialysis days around the normal start time of their dialysis or in the dialysis unit). On dialysis days, the worksheets will be completed prior to or during dialysis, but must be completed prior to dosing of the study drug. During Discontinuation Period, worksheets to be completed on dialysis days only.

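### One visit is enough to enter the Discontinuation Period populations, and the Day 85 withdrawal-scale baseline is itself such a visit, so adverse event denominators can include subjects never assessed afterwards, and the OOWS period maximum includes that baseline

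*SAP*

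**What the plan says.** **Entry rules.** SAP 4.4 defines the Double-blind Discontinuation Safety Population as members of the Double-blind Safety Population "who have at least one visit in the Discontinuation Period". SAP 4.5 defines a narrower Double-blind Discontinuation Population: 12 weeks completed, at least 6 doses in the last 2 weeks, "and have at least one visit in the Discontinuation Period". Disposition in SAP 5.1 matches: "Subjects who entered the Discontinuation Period are those who have at least one visit during the Discontinuation Period".

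**Where the period starts.** SAP Table 4, footnote b: "The End-of-Treatment Visit in the Double-blind Treatment Period corresponds to Day 1 of the Discontinuation Period". Protocol Table 2, footnote b, says that this visit "will be the first dialysis visit following the last dose of study drug", places it on Day 85, and equates it with Day 1 of the Discontinuation Period (DP).

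**What Day 85 is used for.** SAP 3 takes the Day 85 assessment as baseline for both withdrawal scales. SAP 12 gives this as the reason for removing DP Day 1 from the ShOWS comparison.

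**What is counted.** SAP 9.2 defines DP treatment-emergent events as "any adverse event with an onset date after the start of the Discontinuation Period", for up to 2 weeks or until open-label treatment starts. The DP adverse event tables use the Discontinuation Safety population unless stated otherwise; two of them are also shown for the SAP 4.5 population. SAP 10.5 lists DP Days 1, 3, 5, 8, 10 and 12 as OOWS days and tabulates score categories by day, for Days 8 to 12, and for the highest score at any point in the period.

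**The concern.** The Discontinuation Period exists to look for physical dependence, which requires observation after the drug has gone. A rule that is satisfied by the baseline visit does not ensure any such observation. For someone who completes 12 weeks and attends End of Treatment, the visit criterion in SAP 4.5 is met automatically and selects nobody.

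Two consequences follow.

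- Adverse event percentages are divided by a count that can include people with no assessment in the time when a countable event would start. In disposition, those people appear as having entered the period.
- The OOWS period maximum mixes the baseline with the outcome. SAP 8.2.4.3 notes that "the study drug administered during the last dialysis of a particular week is not cleared until the first dialysis of the next week". The OOWS is completed early in the dialysis session (within the first hour in Protocol Table 2, the first 30 minutes in SAP Table 4, each with a 1-hour window). The Day 85 score is therefore taken before that session has cleared the last dose, so signs present on that day are not withdrawal signs.

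**Working it through.** The plan states no DP rate or denominator, so there is no figure to reproduce. The check is of day numbering, then membership, then possible size.

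**1. Which study day is DP Day 1?** If Day 85 is Day 1, study day = 84 + d. If Day 86 is Day 1, study day = 85 + d.

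| DP day d | 1 | 3 | 5 | 8 | 10 | 12 | 14 |
|---|---|---|---|---|---|---|---|
| Day 85 = Day 1 | 85 | 87 | 89 | 92 | 94 | 96 | 98 |
| Day 86 = Day 1 | 86 | 88 | 90 | 93 | 95 | 97 | 99 |

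Scheduled dialysis days run 78, 80, 82, 85, so the weekly pattern continues 87, 89, 92, 94, 96. Only the first row puts the OOWS days on dialysis days and ends on Day 98, the last day given in SAP 2.2.1. SAP 3 (baseline is Day 85) and SAP 12 (baseline is DP Day 1) agree with it.

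The schedule headers do not settle the matter. SAP Table 4 labels the DP column as Days 1 to 14 over study Days 86 to 98, which is 98 − 86 + 1 = 13 days for 14 labels. Protocol Table 2 labels it DP Days 2 to 14 (13 labels) over Days 85 to 98 (14 days).

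**2. Membership.** A subject who attends on Day 85 and never again has one DP visit. That subject meets SAP 4.4, counts as having entered under SAP 5.1, and meets the visit criterion of SAP 4.5. Nothing in those sections says that Day 85 alone is not enough.

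**3. Effect on adverse event percentages.** Let p be the true DP incidence, f the share of the population with only Day 1, and c the fraction of their later events that is still recorded. With equal underlying risk:

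reported rate = p × [1 − f(1 − c)]

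None of p, f or c is in the documents; all values here are assumptions.

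| p = 8% | f = 5% | f = 10% | f = 15% |
|---|---|---|---|
| c = 0 (largest effect) | 7.6% | 7.2% | 6.8% |
| c = 0.5 | 7.8% | 7.6% | 7.4% |

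With the same f and c in both arms, the ratio between arms does not change. With c = 0 and f of 12% on CR845 and 6% on placebo, true rates of 8% and 6% become 8 × 0.88 = 7.04% and 6 × 0.94 = 5.64%: a difference of 1.4 points instead of 2.0.

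**4. Effect on the scales.** An ANCOVA on a day after Day 1 needs a score from that day, so Day-1-only subjects do not enter it. For the OOWS period maximum, adding Day 1 can only raise a subject's maximum or leave it unchanged. Someone scoring 3 on Day 1 and 0 on Days 3 to 12 is reported as a 3. The number scoring 2 or more can therefore only rise through this route. For a Day-1-only subject, the baseline is the whole result.

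**The case against.** The strongest reply is that the SAP may not intend Day 85 to qualify: SAP Table 4 gives it a separate End-of-Treatment column and starts the DP column at Day 86. That reading is possible, and it is why the point concerns the better-supported reading rather than a certainty. It still leaves a header that contradicts its own labels and OOWS days that miss dialysis. Two programmers could build different populations.

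Other limits stand in full.

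- A reader might infer that these subjects are never seen after stopping. They are seen once, at the first dialysis after the last dose; what is missing is any assessment after the baseline.
- A reader might infer that they cannot contribute an event. Protocol 6.5.4.1 collects adverse events to the Follow-up Visit, and related serious events for 30 days after the last dose. Patients who enter the extension return shortly afterwards. SAP 9.2 also assigns an event dated on a period's first day, with no start time, to that period.
- A reader might infer that dilution is worst in the arm with more early stoppers. The documents do not establish this. Footnote b names the End-of-Treatment visit, not Early Termination; Protocol 6.3.1 places the DP after the Early Termination Visit; and SAP 4.5 excludes early stoppers. Protocol 8.9.4 pairs the two visits only as the scale baseline.
- The error is not always downward: for the OOWS maximum, including Day 1 pushes upward.
- Simply requiring a later visit or scale could do harm, because a subject who dies or is hospitalised on Day 86 would drop out of the DP safety tables.

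Against this, Protocol 6.1.1.4 asks for every attempt to conduct the period in early withdrawals, and adverse events are not tested statistically. Both limit the consequences without closing the gap.

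**Conclusion.** The point holds in a limited form. On the reading best supported by footnote b in both schedules, SAP 3, SAP 12 and the OOWS day list, subjects with no assessment after the Day 85 baseline enter the denominators of DP adverse event percentages. Those percentages tend to be too low. The true amount cannot be found from the documents. In the illustration, an 8% rate falls by 0.4 to 1.2 points when 5% to 15% of the population have only Day 1 and none of their later events is recorded, and by half that if half are recorded. A bias between arms would need unequal shares, for which the documents give no evidence.

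The SAP 4.5 population is less exposed, because completion and recent dosing are required. The post-baseline ShOWS and OOWS ANCOVAs are not affected. The OOWS period maximum is a separate fault in the opposite direction: as written, it includes a baseline score taken before the drug is cleared. Both are worth correcting before the data are unblinded, but neither bears on the efficacy conclusions.

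**What to change.** 1. In SAP 10.5, take the OOWS period-maximum category over the days after DP Day 1 and show the Day 1 score beside it. State the denominator.
2. In SAP 4.4, 4.5 and 5.1, state that the Day 85 visit alone does not qualify. Require at least one visit, ShOWS or OOWS assessment, or recorded adverse event (including death or a serious event) after DP Day 1. Show Day-1-only subjects on their own line in disposition. For early stoppers, say which visit is DP Day 1.
3. Reconcile the DP column header in SAP Table 4 with Day 85 as DP Day 1.

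The cost is SAP wording and a slightly smaller population. The adverse event clause in item 2 is needed so that early serious events are not lost. It does make membership depend partly on having an event, which leans the rate slightly upward, so the number admitted only by that clause should be reported.

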4.5 Double-blind Discontinuation Population

The Double-blind Discontinuation Population is defined as the subset of subjects in the Double-blind Safety Population who have completed 12 weeks of treatment, have received at least 6 doses in the 2 weeks prior to the start of the Discontinuation Period, and have at least one visit in the Discontinuation Period. The Double-blind Discontinuation Population will repeat analyses on the endpoints related to drug withdrawal that are also presented for the Double-blind Discontinuation Safety Population.

